Appendix I

Pathology Submission Guidelines

The following items are included in Appendix I:

1. Guidelines for Submission of Pathology Materials
(instructional sheet for Clinical Research Associates [CRAs])
2. Instructional memo to submitting pathologists
3. ECOG-ACRIN Generic Specimen Submission Form (#2981v3)

Guidelines for Submission of Pathology Materials

EA1131 A randomized phase III post-operative trial of platinum-based chemotherapy vs. observation in patients with residual basal-like triple-negative breast cancer following neoadjuvant chemotherapy

Rev. 2/16

The following materials must be submitted within 21 weeks post-surgery.

1. Pathology Submission:

- FFPE tumor tissue block (≥ 1 cm in diameter, > minimal cellularity as per local pathologist determination) from the residual disease on the definitive surgical specimen – submission is **mandatory**.

NOTE: If these criteria cannot be met, please contact the ECOG-ACRIN CBPF ([contact]) to obtain alternative submission requirements.

The following items are to be included with the pathology materials.

Rev. Add6

2. Forms and Reports:

- Copy of institutional surgical pathology report.
- STS generated shipping manifest form.
- CLIA Laboratory Sample Submission Form ([Appendix IV](#))

NOTE: Adequate patient identifying information must be included with every submission. It is strongly recommended that full patient names be provided. The information will be used only to identify patient materials, for interactions between the ECOG-ACRIN CBPF, the central testing laboratory and the site, and will help to expedite any required communications with the institution (including site pathologists).

3. Mail pathology materials to:

ECOG-ACRIN Central Biorepository and Pathology Facility
MD Anderson Cancer Center
Department of Pathology, Unit 085
Tissue Qualification Laboratory for ECOG-ACRIN
Room G1.3598
[name]
[name]

Rev. 6/16

If you have any questions concerning the above instructions or if you anticipate any problems in submitting the required pathology material, contact the Pathology Coordinator at the ECOG-ACRIN CBPF by [contact], by [contact], or by email: [contact].

[name], and [name], PhD
Group Co-Chairs

MEMORANDUM

TO: _____
(Submitting Pathologist)

FROM: [name]., Chair
ECOG-ACRIN Laboratory Science and Pathology Committee

DATE: _____

SUBJECT: Submission of Pathology Materials for EA1131: A randomized phase III post-operative trial of platinum based chemotherapy vs. capecitabine in patients with residual basal-like triple-negative breast cancer following neoadjuvant chemotherapy

A patient has been entered onto an ECOG-ACRIN protocol by _____ (ECOG-ACRIN Investigator). This protocol requires the submission of pathology materials for PAM50 analysis, central review, and defined laboratory research studies.

Return the surgical pathology report(s), the slides and/or blocks and any other required material to the Clinical Research Associate (CRA). The CRA will forward all required pathology materials to the ECOG-ACRIN Central Biorepository and Pathology Facility (CBPF).

Blocks and/or slides submitted for this study will be retained at the ECOG-ACRIN CBPF for future undefined research studies. Paraffin blocks will be returned upon written request for purposes of patient management.

Please note: Since blocks are being used for laboratory studies, in some cases the material may be depleted, and, therefore, the block may not be returned.

If you have any questions regarding this request, please contact the ECOG-ACRIN CBPF at [contact] or [contact].

The ECOG-ACRIN CRA at your institution is:

Name: _____

Address: _____

Phone: _____

Thank you.

ECOG-ACRIN Generic Specimen Submission Form

Form No. 2981v3

Page 1 of 1

Institution Instructions: This form is to be completed and submitted with **all specimens ONLY** if the Sample Tracking System (STS) is not available. **Use one form per patient, per time- point.** All specimens shipped to the laboratory must be listed on this form. Enter all dates as MM/DD/YY. Keep a copy for your files. Retroactively log all specimens into STS once the system is available. **Contact the receiving lab to inform them of shipments that will be sent with this form.**

Protocol Number _____ **Patient ID** _____ **Patient Initials** Last _____ First _____

Date Shipped _____ **Courier** _____ **Courier Tracking Number** _____

Shipped To (Laboratory Name) _____ **Date CRA will log into STS** _____

FORMS AND REPORTS: Include all forms and reports as directed per protocol, e.g., pathology, cytogenetics, flow cytometry, patient consult, etc.

| Required fields for all samples | | | | Additional fields for tissue submissions | | | | Completed by Receiving Lab |
|---|----------|--------------------------------|--|--|---------------|--|-------------------|----------------------------|
| Protocol Specified Timepoint: | | | | | | | | |
| Sample Type <small>(fluid or fresh tissue, include collection tube type)</small> | Quantity | Collection Date and Time 24 HR | | Surgical or Sample ID | Anatomic Site | Disease Status <small>(e.g., primary, mets, normal)</small> | Stain or Fixative | Lab ID |
| | | | | | | | | |
| | | | | | | | | |
| | | | | | | | | |
| | | | | | | | | |

| Fields to be completed if requested per protocol. Refer to the protocol-specific sample submissions for additional fields that may be required. | | | | | |
|---|-----------------------------|--------------------------|----------------------------------|---------------------|---------------|
| Leukemia/Myeloma Studies: | Diagnosis | Intended Treatment Trial | Peripheral WBC Count (x1000) | Peripheral Blasts % | Lymphocytes % |
| | | | | | |
| Study Drug Information: | Therapy Drug Name | Date Drug Administered | Start Time 24 HR | Stop Time 24HR | |
| | | | | | |
| Caloric Intake: | Date of Last Caloric Intake | | Time of Last Caloric Intake 24HR | | |
| | | | | | |

CRA Name _____ **CRA Phone** _____ **CRA Email** _____

Comments

A Randomized Phase III Post-Operative Trial of Platinum Based Chemotherapy Vs. Capecitabine in Patients with Residual Triple-Negative Basal-Like Breast Cancer following Neoadjuvant Chemotherapy

Appendix II

Patient Thank You Letter

We ask that the physician use the template contained in this appendix to prepare a letter thanking the patient for enrolling in this trial. The template is intended as a guide and can be downloaded from the web site at <http://www.ecog.org>. As this is a personal letter, physicians may elect to further tailor the text to their situation.

This small gesture is a part of a broader program being undertaken by ECOG-ACRIN and the NCI to increase awareness of the importance of clinical trials and improve accrual and follow-through. We appreciate your help in this effort.

[PATIENT NAME]

[DATE]

[PATIENT ADDRESS]

Dear [PATIENT SALUTATION],

Thank you for agreeing to take part in this important research study. Many questions remain unanswered in cancer. With the participation of people like you in clinical trials, we may improve treatment and quality of life for those with your type of cancer.

We believe you will receive high quality, complete care. I and my research staff will maintain very close contact with you. This will allow me to provide you with the best care while learning as much as possible to help you and other patients.

On behalf of **[INSTITUTION]** and ECOG-ACRIN, we thank you again and look forward to helping you.

Sincerely,

[PHYSICIAN NAME]

A Randomized Phase III Post-Operative Trial of Platinum Based Chemotherapy Vs. Capecitabine in Patients with Residual Triple-Negative Basal-Like Breast Cancer following Neoadjuvant Chemotherapy

Appendix III

ECOG Performance Status

| | |
|-------------|---|
| PS 0 | Fully active, able to carry on all pre-disease performance without restriction |
| PS 1 | Restricted in physically strenuous activity but ambulatory and able to carry out work of a light or sedentary nature e.g., light house work, office work. |
| PS 2 | Ambulatory and capable of all self-care but unable to carry out any work activities. Up and about more than 50% of waking hours. |
| PS 3 | Capable of only limited self-care, confined to bed or chair more than 50% of waking hours. |
| PS 4 | Completely disabled. Cannot carry on any self-care. Totally confined to bed or chair. |

**A Randomized Phase III Post-Operative Trial of Platinum Based Chemotherapy Vs.
Capecitabine in Patients with Residual Triple-Negative Basal-Like Breast Cancer
following Neoadjuvant Chemotherapy**

Appendix IV

Rev. 6/16

CLIA Laboratory Sample Submission Form

Making Cancer History®

Department of Pathology
Tissue Qualification Laboratory
T [contact] F [contact]
T [contact] (Toll Free)
Unit 0085
[name]
Room G1.3597
[name]

CLIA Laboratory Sample Submission Form

The information on this form is required for results reporting from the CLIA laboratory. This form MUST be completed and submitted with all specimens. Failure to submit this form will result in a delay in specimen processing and a delay in the reporting of results to the ordering physician.

| SECTION I. TRIAL INFORMATION | | | | | |
|--|-----------|---|---|-----------------------------------|-----------|
| ECOG-ACRIN TRIAL NUMBER: _____ | | | ECOG-ACRIN Patient ID: _____ | | |
| Section II. SITE'S TIME ZONE INFORMATION | | | | | |
| Time Zone:  Atlantic  Eastern  Central  Mountain  Pacific  Alaska  Hawaii-Aleutian  Other: _____ Is Daylight Saving Time observed:  Yes  No | | | | | |
| Section III. PATIENT INFORMATION | | | | | |
| Last Name: _____ | | | First Name: _____ | | |
| Date of Birth (MM/DD/YYYY): _____ | | | Gender:  Female  Male | | |
| Section IV. SITE CONTACTS | | | | | |
| Sections A and B must be completed. | | | | | |
| If applicable, has or will the tissue submitted be reviewed by a local pathologist?  Yes  No | | | | | |
| If yes, Section C must be completed and a copy of the local pathology report must be uploaded into Medidata Rave within 5 days of submission of the tissue or per protocol instructions. | | | | | |
| Section A Ordering Physician | | Section B Site CRA or Research Contact | | Section C Pathology Group | |
| Last Name: | | Last Name: | | Last Name (optional): | |
| First Name: | | First Name: | | First Name (optional): | |
| NPI: | | | | | |
| Phone: | | Phone: | | Phone: | |
| Fax: | | Fax: | | Fax (optional): | |
| Institution: | | Institution: | | Institution: | |
| Department: | | Department: | | Department: | |
| Street Address Line 1: | | Street Address Line 1: | | Street Address Line 1: | |
| Street Address Line 2: | | Street Address Line 2: | | Street Address Line 2: | |
| City: | | City: | | City: | |
| State: | Zip Code: | State: | Zip Code: | State: | Zip Code: |
| Physician E-mail (optional): | | Research Contact E-mail (optional): | | Pathologist E-mail (optional): | |
| Office Contact Name (optional): | | Office Contact Name (optional): | | Office Contact Name (optional): | |
| Office Contact E-mail (optional): | | Office Contact E-mail (optional): | | Office Contact E-mail (optional): | |

A Randomized Phase III Post-Operative Trial of Platinum Based Chemotherapy Vs. Capecitabine in Patients with Residual Triple-Negative Basal-Like Breast Cancer following Neoadjuvant Chemotherapy

Appendix V

Rev. 6/16

Patient Pill Calendar

NOTE: This pill calendar is for patients randomized to Arm C ONLY.

Pill Calendar Directions

1. Take your schedule dose of pill
2. If you forget, the missed pills will not be taken later.
3. Please bring the empty bottle or any leftover pills and your pill calendar to your next clinic visit.
4. When taking Capecitabine:
 - Capecitabine pills are to be swallowed whole with water within 30 minutes after a meal
 - Do not crush or cut capecitabine pills

Patient Pill Calendar

This is a calendar on which you are to record the time and number of pills you take each day. You should take your schedule dose of each pill. **Note the times and the number of pills that you take each day.** If you develop any side effects, please record them and anything you would like to tell the doctor in the space provided.

Cycle: _____

Prescribed dosage: _____

Bring any unused pills and your completed pill calendar to your doctor's visits.

| CYCLE DAY | Date | | | Times Pills Taken | | Number of Pills Taken | | Use the space below to make notes about things you would like to tell the doctor (including unusual symptoms you experience, other medicine you have taken and anything else you think would be of interest.) |
|-----------|----------------------|--|--|-------------------|----|-----------------------|----|---|
| | (Month / Day / Year) | | | AM | PM | AM | PM | |
| 1 | | | | | | | | |
| 2 | | | | | | | | |
| 3 | | | | | | | | |
| 4 | | | | | | | | |
| 5 | | | | | | | | |
| 6 | | | | | | | | |
| 7 | | | | | | | | |
| 8 | | | | | | | | |
| 9 | | | | | | | | |
| 10 | | | | | | | | |
| 11 | | | | | | | | |
| 12 | | | | | | | | |
| 13 | | | | | | | | |
| 14 | | | | | | | | |

Patient Signature: _____ Date: _____

Number of pills returned: _____

Administrator Signature: _____ Date: _____

A Randomized Phase III Post-Operative Trial of Platinum Based Chemotherapy Vs. Capecitabine in Patients with Residual Triple-Negative Basal-Like Breast Cancer following Neoadjuvant Chemotherapy

Rev. Add#5

Appendix VI

Ancillary for Tobacco Use Assessment: EAQ16T

Study Co-Chairs: [name], [name], [name], [name], [name]

Patients registered to selected ECOG-ACRIN trials are eligible to participate in this ancillary study, once the appropriate amendment incorporating the study is activated.

The Ancillary for Tobacco Use Assessment is a project that seeks to address questions about patient-reported tobacco use and smoking behaviors that may span several studies and/or diseases. The tobacco use ancillary is embedded into parent protocols, with participation in the ancillary informed in the parent consent form and participation determined via providing email address to the sites. The general objectives of the tobacco use ancillary are not specific to any single parent protocol; however, specific objectives may be included in the parent or related parent protocols.

A significant proportion of cancer patients are current smokers at the time of cancer diagnosis,¹⁻⁵ and there are known risks associated with continued smoking following cancer diagnosis. These include decreased survival time; increased complications from surgery, radiation, and chemotherapy; and increased risk of second primary tumors.⁶⁻¹¹ As such, the National Comprehensive Cancer Network (NCCN), the American Association of Cancer Research (AACR) and the American Society of Clinical Oncology (ASCO) have identified persistent smoking as a modifiable risk factor and recommend cessation counseling for cancer patients who smoke. Although evidence-based guidelines for treating tobacco dependence exist,¹² they have not yet been well-integrated into cancer care settings. Moreover, knowledge regarding the scope and patterns of tobacco use among cancer patients is limited. As a critical step in closing this knowledge gap, the NCI-AACR Cancer Patient Tobacco Use Assessment Task Force developed the Cancer Patient Tobacco Use^{1-4,13,14} Questionnaire (C-TUQ). Through this ancillary, the modified C-TUQ measures will be administered to participants enrolling in selected Phase II and Phase III ECOG ACRIN (EA) therapeutic trials.

The major questions may be summarized:

1. What is the smoking status of cancer patients enrolled on EA clinical trials?
2. Do patients quit smoking or try to quit smoking after receiving a cancer diagnosis?
3. What forms of tobacco use do patients engage in?
4. What assistance do patients use or receive to try to quit?
5. How does tobacco use, other forms of tobacco use, and/or environmental tobacco exposure affect patient's treatment toxicity, patient-reported physical and psychological symptoms, trial adherence, and therapeutic outcomes?

When patients consent to participate, they will be asked to provide a contact email address and that address along with their registration information will be sent directly from the parent trial's registration system to ECOG-ACRIN Systems for Easy Entry of Patient Reported Outcomes (EASEE-PRO), and the patient will be automatically registered into EASEE-PRO for participation. To activate their account for self-directed web entry of surveys, the system will send an activation message to the contact email address that will explain how to activate their account for self-directed web entry of surveys. After their account is activated, the patient will be

able to complete questionnaires using a secure browser interface from any web enabled computer, tablet, or mobile device.

Measures

The selected Core and Extension C-TUQ items will be assessed. The 4-item Short Form PROMIS® for anxiety and depression, the Lung Cancer Stigma Scale, and six symptom items (general pain, fatigue, nausea, cough, insomnia, shortness of breath) from FACIT (Functional Assessment of Chronic Illness Therapy)) together with modifications of these same six questions to address the degree of bother associated with each symptom will be administered as well. Additionally, we will ask participants’ perceptions of how smoking improves or worsens each of the six symptom experience. All these items will be compiled into Survey of Tobacco Use (STU) (baseline and follow-up).

Contents and Corresponding Questions in Survey of Tobacco Use (STU)

| Dimension | Source of Measures | Baseline STU | Follow-up STU |
|---|------------------------------------|--------------|---------------|
| Basic Tobacco Use Information | C-TUQ | Q1 – Q5 | Q1 – Q2 |
| Tobacco Use in Relation to Cancer Diagnosis and Treatment | C-TUQ | Q6 – Q7 | Q3 |
| Smoking Cessation, Cessation Products, and Assistance Methods | C-TUQ | Q8 – Q13 | Q4 – Q9 |
| Use of Other Products | C-TUQ | Q14 | Q10 |
| Second-Hand Smoke Exposure | C-TUQ | Q15 – Q16 | Q11 – Q12 |
| Psychological Symptoms | PROMIS Lung Cancer Stigma Scale | Q17 – Q18 | Q13 – Q14 |
| Physical Symptoms | FACIT | Q19 | Q15 |
| Sociodemographics | | Q20 – 21 | |

NOTE: In order to minimize ambiguity and assure that patients are oriented to answer appropriately, the specific phrasing of items may vary depending specific cancer type and treatment.

Tobacco Use. The selected Core and Extension C-TUQ items (from categories of Basic Tobacco Use Information, Tobacco Use in Relation to Cancer Diagnosis and Treatment, Smoking Cessation/Cessation Products/Assistance Methods, Use of Other Products, and Second-Hand Smoke Exposure) will be assessed in the baseline and follow-up Survey of Tobacco Use.

Oncology Provider Assistance. C-TUQ Question 13 assesses “cancer doctors” Advise. We will add 4 As to assess participants’ reported 5As (Ask (Q12a), Advise (Q12b), Assess (Q12c), Assist (Q12d-Q12f), and Arrange follow-up (Q12g), as in Baseline STU).⁸⁰

Psychological Symptom Assessment. Anxiety & Depression: *(The Patient Reported Outcomes Measurement Information System (PROMIS®)).* We will administer the 4-item Short Form PROMIS® for anxiety and depression (Q17 in Baseline STU). **Stigma:** The Lung Cancer Stigma scale measures the extent to which shame is internalized (Q18 in Baseline STU).⁸¹

Physical Symptom Assessment *Physical Symptom Assessment (Functional Assessment of Chronic Illness Therapy (FACIT)).* FACIT, a measurement system with a collection of quality-of-life questionnaires, expands the more familiar FACT (Functional Assessment of Cancer Therapy) questionnaires into other chronic illness and conditions. FACIT consists of many

individual questions to assess various symptoms from the patient perspective. We will use 6 FACIT items, selected based on the therapeutic regimens, expected toxicity, and malignancy type of the parent trials. In addition, we have created modifications of these same six questions to address the degree of bother associated with each symptom” The symptoms of general pain, fatigue, nausea, cough, sleep difficulty, and shortness of breath will be assessed, first using the standard and validated FACT item, and then asking the degree of “bother” imposed by each symptom, on the same 5-point scale. These clusters of symptoms were specifically chosen based on potential interactions between tobacco use and longitudinal symptoms.

Sociodemographic Variables. Sociodemographic variables, including age, sex, zip code, and race/ethnicity are collected for all NCTN trial participants at registration. At baseline, participants will provide information on marital status (Q20 in Baseline STU) and education level (Q21 in Baseline STU) as part of the tobacco supplemental assessment.

Cancer Treatment Variables. Clinical variables including date of diagnosis, malignancy type (smoking related vs. non-smoking related, cancer stage), and treatment details (i.e. types and dates of surgery, chemotherapy, and/or radiation received), along with disease status and survival, will be captured in Medidata Rave via the parent protocol and will be available for analysis of the ancillary. Provider-assessed adverse events will also be captured via the parent protocol in Medidata Rave, using case report forms commonly used across the NCTN and using standard data elements.

Assessments

All items in Survey of Tobacco Use will be administered using the EASEE-PRO system. The advantage of our virtual electronic data capture system is that our proposed assessments will not be limited to, or dependent upon, patient trial visits. Confidential and potentially stigmatizing information can be provided without requiring direct contact with the care team.

Timing of Assessments

Given the critical questions that remain¹³ about the timing of conducting tobacco use assessments, we have carefully chosen to collect tobacco assessment data at trial enrollment, 3 and 6 month follow-up. For tobacco treatment trials, 6 month follow-up is the recommended primary outcome time point. By 6 month follow-up, most cancer treatment-related quitting activity⁶², cancer treatment initiation of therapy, and FDA-approved smoking cessation medication regimens will be completed. Adverse events during treatment will have been observed.

Statistical Considerations and Analysis Plans

The analysis plans described below are planned for a combined analysis of the data from the 8 selected ECOG-ACRIN trials. Consistency in the effects over the studies would be examined in this analysis.

1. CHANGES IN SMOKING STATUS AND EXPOSURE. At baseline, combustible tobacco use (1a) will be characterized by smoking status (never smoker, former smoker, and current smoker based on Baseline STU Qs 1 and 5), other forms of tobacco use (1b) will be a composite variable determined by non-cigarette items (based on Baseline STU Q7 and Q14), and environmental tobacco smoke (ETS) level (1c) will be determined by current household and work exposure (Baseline STU Qs 15-16). At follow-up, combustible tobacco use (1a) will be examined by smoking status (Follow-up STU Qs 1 and 2), other forms of tobacco use (1b) will be determined by Follow-up STU Q10, and ETS level (1c) will be determined by 30 day household and work exposure (Follow-up STU Qs 11-12). We will examine tobacco use at baseline, 3 and 6 month follow-up, and change in status (abstinence in combustible tobacco, abstinence of other forms of tobacco use, and change

- in exposure to smoke-free home and work) using summary statistics (frequency and proportion). We will explore the effects of sociodemographic and cancer treatment factors on smoking status using logistic regression (comparing smokers and non-smokers). We will also evaluate factors associated with changes in smoking status.
2. **TREATMENT TOXICITY.** The selected trials capture information about adverse events during treatment using NCI's Common Terminology Criteria for Adverse Events, Version 4. Toxicities are measured at each treatment visit and graded according to severity, with grade 1 corresponding to mild toxicity and grade 5 signifying a lethal adverse event. We will determine each patient's worst degree toxicity across all event types and treatment visits and will compare the distribution of worst degree grades between smokers and non-smokers and between patients with environmental tobacco exposure and those without exposure using exact tests. We will also examine the distribution of worst degree grades between users with different form of tobacco use. In addition, we will explore the effects of tobacco use on dose modifications (yes vs. no) using logistic regression, with each patient's dose modification status determined across all treatment visits.
 3. **SYMPTOM BURDEN.** Tobacco variables will be conceptualized as described in the section of **CHANGES IN SMOKING STATUS AND EXPOSURE**. Tobacco use status (as measured at baseline, 3 and 6 months follow-up) will be compared to physical and psychological symptom burden (as measured at each corresponding time points). At 3 and 6 months follow-up, we will also examine the association between tobacco use changes and changes in symptom burden. We will explore the effects of sociodemographic and cancer treatment factors on symptom burden using repeated measures mixed effects models. As an example of statistical power, we consider the PROMIS SF-4 depression measure. We assume that 1500 patients will be enrolled across the 8 parent studies over 13 months, and that 20% are smokers. We assume that 85% of patients will have assessments at 6 months. Given groups of these sizes (26 quitters and 230 still-smokers) and standard deviation of 4.08 for the PROMIS SF-4 depression scale, there will be 83% power to detect a difference in change scores of 2.5 between groups using a two-sample t-test with Type I error of 5%. The minimally important difference for this instrument is 2.2.⁷⁹
 4. **CESSATION PATTERNS AND TREATMENT.** At baseline we will explore pre-treatment combustible tobacco use patterns (STU Q6a and Q6b), quitting behaviors (STU Q13), behavioral program utilization (STU Q11) and oncology provider support (5As, STU Q12), and smoking cessation medication use (STU Q10). At follow-up we will explore post-treatment combustible tobacco use patterns (STU Q3a-Q3e), quitting behaviors (STU Q9), behavioral program utilization (STU, Q7) and oncology provider support (5As, STU Q8), and smoking cessation medication use (STU Q6). We will explore the effects of sociodemographic and cancer treatment factors on these variables. We will examine associations of quitting behaviors and behavioral and medication utilization with tobacco use status (as outlined in the section of **CHANGES IN SMOKING STATUS AND EXPOSURE**) at baseline and on respective 3 and 6 month tobacco outcomes. These analyses will be descriptive in nature. Summary statistics (frequency, proportions, and 95% confidence intervals) will be used.
 5. **TRIAL OUTCOMES.** We will compare treatment duration between smokers and non-smokers and between patients with environmental tobacco exposure and those without exposure. Cumulative incidence/competing risk methods will be used to estimate time to treatment discontinuation for adverse events, disease progression, completion per protocol, or other causes. Gray's test will be used to test for differences in the cumulative incidence distributions.⁷⁸ Differences in the distribution of reasons for discontinuation of treatment will be examined using exact tests. Relative dose intensity is defined as the ratio of actually delivered dose intensity to the planned dose intensity. The effects of tobacco use and

exposure on relative dose intensity ($\geq 90\%$ vs. $< 90\%$) will be explored using logistic regression. Differences in the primary endpoint and important secondary endpoints will be examined using log rank test and exact test (as appropriate).

Data collected in the tobacco use project will support a range of analyses. Precise estimates of power will depend on the prevalence of smoking at baseline among study participants, the proportion whose smoking status changes, and the duration and adequacy of follow-up.

References

1. Yi, Yang P, Parkinson J, Zhao X, Wampfler JA, Ebbert JO, Sloan JA. The relationship between cigarette smoking and quality of life after lung cancer diagnosis. *Chest*. 2004; 126(6):1733-1741. doi: 10.1378/chest.126.6.1733.
2. Gritz E. Rationale for Treating Tobacco Dependence in the Cancer Setting. Conference presentation at: Treating Tobacco Dependence at the National Cancer Institute's Cancer Centers. December 2009.
6. Dresler CM. Is it more important to quit smoking than which chemotherapy is used? *Lung Cancer*. 2003;39(2): 119-124.

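### Appendix VI defines other tobacco use by two baseline items but one follow-up item, so abstinence from it can be overstated; smoke exposure is also described over different time windows

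*Combined protocol and SAP*

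**What the plan says.** Section 9.6.3 refers the statistics for the tobacco survey to Appendix VI. Item 1 of the analysis plans there defines three exposures: combustible tobacco (1a), other tobacco (1b) and environmental tobacco smoke (1c).

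For 1b, the baseline rule is "other forms of tobacco use (1b) will be a composite variable determined by non-cigarette items (based on Baseline STU Q7 and Q14"), and the follow-up rule is "other forms of tobacco use (1b) will be determined by Follow-up STU Q10".

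For 1c, the baseline level "will be determined by current household and work exposure (Baseline STU Qs 15-16"), while at follow-up "ETS level (1c) will be determined by 30 day household and work exposure (Follow-up STU Qs 11-12").

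Item 1 then summarises, by frequency and proportion, "change in status (abstinence in combustible tobacco, abstinence of other forms of tobacco use, and change" in exposure to smoke-free home and work. Item 3 relates changes in tobacco use to changes in symptom burden at 3 and 6 months.

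The contents table of the survey (Appendix VI, repeated in Section 5.6.1) gives the baseline and follow-up question numbers for each dimension. Two rows matter here: "Use of Other Products | C-TUQ | Q14 | Q10" and "Tobacco Use in Relation to Cancer Diagnosis and Treatment | C-TUQ | Q6 – Q7 | Q3".

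**The concern.** A change in status is interpretable only if status is measured in the same way at both times. For other tobacco use, the baseline definition has a component, Q7, that the follow-up definition lacks. A patient who enters the baseline user group through that component alone could leave it at follow-up because nothing asks about the product again, and would then be summarised as abstinent.

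Two results would be affected. The proportion abstinent from other tobacco would be too high. Any comparison of symptom change between abstainers and continuing users would be pulled toward zero, because the abstainer group would include people who did not change.

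For smoke exposure the question is narrower. The plan describes baseline exposure as current and follow-up exposure as covering 30 days, so part of an apparent change may come from the window.

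**Working it through.** **1. Is there a plan figure to reproduce?** None exists for abstinence from other tobacco or for change in smoke exposure. The only power figure in this part of Appendix VI (item 3, 83%) concerns depression scores in cigarette quitters: 26 quitters, 230 still-smokers, SD 4.08, difference 2.5, type I error 5%.

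- Standard error = 4.08 × √(1/26 + 1/230) = 0.844.
- Power ≈ Φ(2.5/0.844 − 1.96) = 0.842 (0.839 with the t distribution).

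This agrees with the plan closely enough, and the present point does not affect it.

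**2. Do the items match?** Setting the definitions in item 1 against the contents table:

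| Exposure | Baseline items | Follow-up items | Contents table |
|---|---|---|---|
| 1a combustible | Q1, Q5 | Q1, Q2 | One dimension at both times (Q1–Q5; Q1–Q2) |
| 1b other tobacco | Q7, Q14 | Q10 | Q14 pairs with Q10; Q7 is in another dimension, with follow-up Q3 |
| 1c smoke exposure | Q15–16 | Q11–12 | One dimension at both times |

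Only 1b has a baseline item from a dimension that its follow-up definition does not draw on. Item 4 does not fill the gap: it uses baseline Q6a and Q6b and follow-up Q3a to Q3e, all for patterns of combustible use. As written, baseline Q7 has no counterpart in the follow-up derivation of 1b, and no rule restricts the change measure to the common items.

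**3. When does this produce false abstinence?** Three conditions are needed:

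- the composite scores a patient positive on Q7 or Q14;
- some baseline users are positive on Q7 only;
- Q10 does not cover the product that made them positive.

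Let s be the share of baseline users who meet the last two conditions, and q the true quit rate, taken as the same in all baseline users. Then

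- apparent abstinence A = q + (1 − q)s;
- false share of apparent abstainers F = (1 − q)s / A;
- fraction of a true abstainer-versus-continuer contrast that remains = q / A, if false abstainers have the same average symptom change as continuing users.

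With no true quitting (q = 0), A = s: 0%, 5%, 10%, 20% or 30% for those values of s.

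With q = 10%, a rate borrowed from the plan's cigarette figures (26/256 = 10.2%):

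| s (assumed) | A | F | Contrast remaining |
|---|---|---|---|
| 0% | 10% | 0% | 1.00 |
| 5% | 0.10 + 0.90 × 0.05 = 14.5% | 0.045/0.145 = 31% | 0.69 |
| 10% | 0.10 + 0.90 × 0.10 = 19% | 0.09/0.19 = 47% | 0.53 |
| 20% | 0.10 + 0.90 × 0.20 = 28% | 0.18/0.28 = 64% | 0.36 |
| 30% | 0.10 + 0.90 × 0.30 = 37% | 0.27/0.37 = 73% | 0.27 |

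Every value of s is an assumption. The documents give none, and 0 is possible. The table shows that when true quitters are few, even a small s matters.

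**4. Smoke exposure.** The items pair correctly in the contents table; only the described window differs. If the baseline window is shorter than 30 days, the longer follow-up window would tend to find more exposure and so understate a move to smoke-free. If it is the same or longer, that argument fails. The question wording is not given, so no direction can be assigned.

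**The case against.** The strongest reply is that the consequence rests on text that is not in the documents. The contents table gives dimension names and question numbers, not wording or response options. Follow-up Q10 may cover every product in baseline Q7 and Q14. The word composite does not state an either-item rule: Q7 may supply timing or history that refines Q14, and then nobody would be positive on Q7 alone. Different items at the two times are also not a fault in themselves, since combustible status does the same, as is natural when baseline must separate never, former and current smokers.

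This stands as far as size is concerned. A reader might infer that patients with unchanged behaviour are in fact being counted as quitters and that abstinence is overstated. The documents do not support that, because s may be 0. A reader might also infer that the exposure windows create false moves to smoke-free. That is not supported either: exposure has no quit status, and the direction is unknown.

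The reply does not remove the mismatch. Combustible use draws on one dimension at both times; other tobacco use does not. If part of Q3 does cover non-cigarette products, items 1 and 4 omit that use of it. If Q10 covers all of Q7's products, the plan should say so.

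The reply is also right about importance. The note to Section 2.5 calls the tobacco objectives ancillary, plans a combined analysis, and keeps these data out of the clinical study report. Item 1 names abstinence from other tobacco only for summary statistics, and current use is also reported at each time point.

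**Conclusion.** The point holds as a mismatch in definition with a possible, one-directional bias. Baseline and follow-up other tobacco use are not defined on matched items, and abstinence is derived from them without a harmonising rule. If the composite scores on either item, leaving out Q7's counterpart can only make a continuing user look abstinent; it cannot make a quitter look like a user.

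The size cannot be established. With no true quitting, false abstinence equals s, from 0% to, by assumption, 30%. With 10% true quitting, s = 10% would give 19% apparent abstinence, of which 47% is false.

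The difference in exposure windows is a secondary point, with unknown direction and size.

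Importance is low: an exploratory ancillary analysis over 8 trials, with no bearing on this trial's treatment comparison or its clinical study report.

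**What to change.** In Appendix VI, item 1:

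- Derive abstinence from, or change in, other tobacco use from the paired items, baseline Q14 and follow-up Q10, after checking in the questionnaires that the two cover the same products. If follow-up Q3 covers non-cigarette products, the alternative is to add the relevant part of it to the follow-up definition as Q7's counterpart.
- Keep the Q7 and Q14 composite for describing baseline use only, and state how it is scored.
- For smoke exposure, use the same time window at both times, or confirm from the question wording that the items are equivalent. Adjusting follow-up exposure for baseline exposure is not a substitute, because it does not align the windows.

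For other tobacco use the cost is analysis-plan wording, with no new data. The small downside of the paired-item rule is that patients identified only by Q7 leave the change analysis. For exposure, confirming equivalence is likewise a check of wording.
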